This study will recruit adolescents between ages 14-17, inclusive, who are able to read and speak English, who have a negative or unknown HIV status; and who have engaged in high-risk sexual activity in the last 12 months.

The study will also recruit adults who are able to read and speak English and who are parent or guardian to an adolescent who is between ages 14-17, inclusive.

Adolescents and parents will be recruited from four U.S. cities: Baltimore, MD; Chicago, IL; Denver, CO; and, Tampa, FL. These cities have diverse populations, high rates of incident HIV infection among adolescents and young adults, and/or demonstrated success in recruiting minor adolescents for biomedical HIV research.

RANDOMIZATION:

Adolescents will be randomized in a 1:1:1 ratio into 1 of the 3 consent conditions using block randomization with block size k=3 (so that in every 3 subjects, exactly 1 is allocated to each condition). The randomization will be stratified by study site and sex assigned at birth. Within study site, sex assigned at birth, and consent condition, the order in which the hypothetical trials will be presented to adolescents will be block randomized with block size k=2. A subset of 6-8 adolescents (3-4 males and 3-4 females) at each site will be selected for participation in the debriefing interview.

Enrollment of parents will be restricted to approximately 15 parents of adolescent natal males and 15 parents of natal adolescent females at each study site. Parents will indicate the acceptability of each of the three consent conditions for each of the two hypothetical trials. Independently of the gender strata, the order of hypothetical trial presentation will be block randomized with block size k=2. Separately for each hypothetical trial, the order of evaluation of the three consent conditions will be randomized so that each ordering is equally likely. A subset of 6-8 parents at each site (for total of 24-32) will be selected for participation in the debriefing interview.

SPECIFIC AIMS:

1. Describe how consent conditions influence high-risk minor adolescents' WTP in a hypothetical biomedical HIV prevention trial.
2. Describe how consent conditions affect parents' WTS a hypothetical biomedical HIV prevention study.
3. Describe the effects of the study agent (stage of development and method of delivery) on high-risk minor adolescents' WTP and parents' WTS a hypothetical biomedical HIV prevention trial.

STUDY PROCEDURES

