Routine team monitoring of any adverse impact of the study will rely on the ATN Query & Notification System (QNS), a real-time, web-based interactive reporting system. Sites will record and enter in the ATN QNS, all untoward events associated with study participation, which will be reviewed on the Study Team Review Committee's monitoring calls. Routine team monitoring of protocol deviations will occur through Qualtrics. RS will enter any deviations into the Protocol Deviations Survey, which will automatically notify the central IRB site PI, [name], and her study team.

STUDY SCHEMAS

[figure not shown]

Figure 1A. Study schema, adolescent participants

[figure not shown]

Figure 1B. Study schema, parent participants

Legend for both figures:

- CC – Consent Condition
- CC 1: Adolescent self-consent
- CC 2: Adult permission required
- CC 3: Parental permission required
- CAB – Cabotegravir (an HIV treatment medication)
- CASI – Computer assisted self-interview
- RS- Research Staff
- WTP – Willingness to participate in the study
- UBACC – UCSD Brief Assessment of Capacity of Consent

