2.0 SPECIFIC AIMS

The purpose of this study is to examine how the consent process affects the acceptability of participation in biomedical HIV prevention trials, from the perspective of behaviorally high-risk minors and the parents of minor adolescents. Acceptability will be measured by adolescents' willingness to participate (WTP) in and parents' willingness to support (WTS) their adolescent's participation in two hypothetical biomedical HIV prevention trials that are modeled after PrEP studies that included minors.

Aim 1: Describe how consent conditions influence high-risk minor adolescents' WTP in a hypothetical biomedical HIV prevention trial.

Primary Hypothesis: Adolescents assigned to the self-consent model will have the highest WTP scores, followed by those assigned to the adult permission model, and finally those assigned to the required parent permission consent model.

Additional sub-aims:

- Determine whether concern about HIV, capacity to consent, family context and sociodemographic characteristics moderate the relationship between consent condition and WTP scores.
- Describe high-risk minors' perceptions of the risks and benefits of parental consent, how they anticipate the different models of consent would influence their WTP in prevention trials, and whether shared-decision making between minors and parents is feasible.

Aim 2: Describe the acceptability of different consent conditions, from the parent perspective.

Primary Hypothesis: The parental permission required scenario will be the most acceptable to parents, followed by the adult permission model, and finally the adolescent self-consent model.

Additional sub-aims:

- Determine whether concern about HIV, capacity to consent, and sociodemographic characteristics moderate the relationship between consent condition and acceptability.
- Describe parents' attitudes toward the various consent models, their perceptions of the risks and benefits of each model, and their conceptualization of a shared decision making process for consent.

Aim 3: Describe the effects of the study agent (stage of development and method of delivery) on high-risk minor adolescents' WTP scores and parents' acceptability scores

Primary Hypothesis: WTP and acceptability scores will be higher for the study of an oral medication that is already FDA-approved for adults compared to study of a topical agent that is still under investigation.

Additional sub-aims:

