3.0 STUDY DESIGN

This study will use a quasi-experimental design to explore how the informed consent process affects the acceptability of biomedical HIV prevention trials, from the perspective of behaviorally high-risk minor adolescents and the parents of minor adolescents. All study participants will complete a computer assisted self-interview (CASI) that collects demographic, social, behavioral, and attitudinal measures. Adolescent participants will undergo a simulated consent process for each of two hypothetical studies based on their randomized consent condition (Appendix II). Parent Participants will undergo a simulated consent process that mimics what their own adolescent would hear while consenting for each of the two hypothetical studies. After each hypothetical study, parent participants will complete a CASI with three vignettes that describe each of the three possible consent conditions. Parents will rate the acceptability of each vignette. The order of vignettes, and the order of the two hypothetical studies, is varied to reduce the possibility of ordering bias. Hypothetical Study 1, modeled after ATN 113, is an open-label study of oral TDF-FTC and hypothetical Study 2, modeled after HPTN 077, is a Phase IIa trial of an injectable HIV integrase inhibitor.

Eligible adolescent participants will complete a demographic questionnaire, then be lead by RS through a simulated study consent process for one of two hypothetical studies. The consent process will be consistent with their randomly assigned consent condition. After completing the simulated consent process, the adolescent will complete a CASI assessing adolescents' WTP and will work with RS to complete the UCSD Brief Assessment of Capacity to Consent (UBACC)²⁵. The

simulated consent process and follow-up assessments will then be completed for the second hypothetical study. After the second UBACC, the adolescent will complete overall WTP, medical mistrust, and end of study questions.

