10.2 Study Endpoints

There are primary key endpoints for this study:

1. Adolescent WTP scores (values 1 through 5) converted from a Likert scale (definitely not participate, probably not participate, might or might not participate, probably participate, definitely participate). Adolescent WTP scores are the measured adolescent response to the question: "If offered the chance, how likely would you be to participate in the first/second study?"
2. Parental WTS scores are the measured parent response to three vignettes. Parents are asked the same vignettes after listening to Study 1 and Study 2. The vignettes and study orders are varied.
 - a. Vignette 1 states: "Imagine your teen wants to join the study we just described. Your teen asks you to come to the research clinic with them. You are given information about the study, and have the opportunity to ask any questions you want to ask. After your questions are answered, you are asked to give your permission for your teen to join the study. In this approach to consent, you have the final say about whether your teen can join the study. How acceptable is this approach to research consent?"
 - b. Vignette 2 states: "Imagine your teen wants to join the study we just described. Your teen comes to the research clinic on their own. They read the consent form, and have an opportunity to ask questions. Your teen is required to have an adult's permission to sign up for the study. They can choose to ask either you or a neutral adult, called an "ombudsman." The ombudsman is not in charge of the study; the ombudsman's job is to ensure your teen understands the research study, and to help your teen think about the risks and benefits of joining the study. Your teen would need either your permission OR the ombudsman's permission to join the study. In this approach to consent, your teen must have an adult's permission to join the study; your teen would be able to choose whether to seek permission from you or the ombudsman. How acceptable is this approach to research consent?"

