APPENDIX I

Schedule of Evaluations

Evaluation (Procedure)	Screening Day 0	Pre-Entry Day 1-3	Entry Day XX
Determine eligibility and collect contact information using the web-based screening tool	X		
Contact eligible adolescents/parents to schedule their visit		X	
Participant consents to participate in the study			X
The participant will complete the demographic, social, and attitudinal measures by audio computer-assisted self-interview (CASI).			X
Participant will undergo a simulated consent process for hypothetical Study 1, modeled after ATN 113, is an open-label study of oral TDF-FTC.			X
Participant will complete the WTP/WTS scale(s) via CASI			X
The RS will administer the UCSD Brief Assessment of Capacity to Consent (UBACC) for hypothetical Study 1.			X
Participant will undergo a simulated consent process for hypothetical Study 2, modeled after HPTN 077, a Phase IIa trial of oral + injectable cabotegravir.			X
Participant will complete the WTP/WTS scale(s) via CASI			X
The RS will administer the UCSD Brief Assessment of Capacity to Consent (UBACC) for hypothetical Study 2.			X
Willing participants will participate in a debriefing interview, which will begin immediately after their 2 nd UBACC.			X

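### Do the word topical in the Aim 3 hypothesis, and averaging the parents' trial-type effect over three vignettes, undermine the planned comparison?

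*Combined protocol and SAP*

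**What the plan says.** In section 2.0 the comparator of the Aim 3 primary hypothesis is set by the phrase "compared to study of a topical agent that is still under investigation". The prediction itself, stated just before that phrase, is that "WTP and acceptability scores will be higher for the study of an oral medication that is already FDA-approved for adults". The same section says acceptability is measured by willingness regarding "participation in two hypothetical biomedical HIV prevention trials that are modeled after PrEP studies that included minors".

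Study 1 is an open-label study of oral TDF-FTC. Study 2 is described as follows:

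- Sections 3.0 and 10.1: it "is a Phase IIa trial of an injectable HIV integrase inhibitor".
- Appendix I: "a Phase IIa trial of oral + injectable cabotegravir".
- Legend to the study schemas: the drug listed is "Cabotegravir (an HIV treatment medication").

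Aim 3 in the abstract refers only to the study agent and to parents' "WTS a hypothetical biomedical HIV prevention trial"; it names no product.

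Under section 10.2, parents rate three vignettes after each study. Each opens with "Imagine your teen wants to join the study we just described" and ends by asking how acceptable that approach to consent is, on a 5-point scale. Section 10.4.1 fits a linear mixed model with consent condition, trial type, sex assigned at birth and site as fixed effects and a random participant intercept. Heterogeneity of the trial-type effect is examined by site. No consent-condition-by-trial term is listed.

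**The concern.** Aim 3 concerns stage of development and method of delivery, and method of delivery is the attribute its hypothesis misnames. Read literally, the hypothesis describes a comparison that no participant is shown. A reader could suspect that the wrong contrast will be tested, or that Study 2 was changed and the analysis was not.

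The parent side raises a second doubt. The endpoint rates the consent approach, so it reflects support for the study itself only indirectly. The listed model gives one trial-type effect pooled over three vignettes. If the agent mattered under only one consent condition, the pooled estimate would be diluted, and opposite effects would cancel. Section 3.4.2 also lists a more direct item, how likely the parent is to let the teen enrol. Table 2 omits that item, and no trial-type analysis of it is stated.

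**Working it through.** **The plan's own figure.** The only power statement (section 10.3) is for consent condition among adolescents: N = 120, 7 predictors, f² = 0.09, 80% power. With a noncentral F test, 2 and 120 − 7 − 1 = 112 degrees of freedom, and noncentrality 0.09 × (2 + 112 + 1) = 10.35, power is 0.8185, which agrees. No power is given for trial type, so the word topical enters no calculation.

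**Wording.** Set side by side, section 2.0 says topical, sections 3.0 and 10.1 say injectable, and Appendix I says oral plus injectable. Vaginal products appear only as background in sections 1.1 and 1.2. The trial-type variable in section 10.4.1 takes two values, the two hypothetical studies. Renaming the second leaves the data, model, estimate and p-value unchanged.

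**Averaging.** With six complete ratings per parent and no interaction term, the trial-type coefficient is the mean of the three vignette-specific differences. Effects (d, 0, 0) average d/3; (0.3, 0, −0.3) averages 0.

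The documents give no SD or correlation for parent scores. Assume SD 1.2, correlation r = 0.6 between the two ratings of the same vignette, n = 144, and correlation c between Study 1 minus Study 2 differences on different vignettes.

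- Variance of one difference: v = 2 × 1.2² × (1 − 0.6) = 1.152.
- One vignette: SE = √(1.152/144) = 0.089.
- Average: SE = √(v(1 + 2c)/(3n)).
- 2-df interaction test: noncentrality n × Σ(dᵢ − mean)²/(v(1 − c)).

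| | c = 0 | c = 0.25 | c = 0.5 |
|---|---|---|---|
| SE of average | 0.052 | 0.063 | 0.073 |
| Power of average, effect −0.2 on all three | 97% | 89% | 78% |
| Power of average, effect −0.4 on one only | 73% | 56% | 45% |
| Power of 2-df interaction, −0.4 on one only | 91% | 97% | >99% |
| Spread for 80% interaction power, equally spaced effects | 0.39 | 0.34 | 0.28 |

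A common effect of −0.2 tested on one vignette alone has 61% power. Over SD 1.0 to 1.4, r 0.4 to 0.8, c 0 to 0.5 and 120 to 144 parents (15 + 15 per site in section 3.3, 18 + 18 in section 5.2.2, four sites), the SE of the average runs from 0.030 to 0.114, that for one vignette from 0.053 to 0.140, and the interaction spread from 0.16 to 0.61.

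**Limits of these figures.** They describe a paired-difference test, whereas the plan uses a random intercept only, which pools all six ratings into one residual variance. Assume correlations between different vignettes of 0.4 within a trial and 0.4 across trials (c = 0), or 0.5 and 0.3 (c = 0.5). The mean of the 15 pairwise correlations is then (3 × 0.6 + 6 × 0.4 + 6 × 0.4)/15 = 0.44, and likewise (1.8 + 3.0 + 1.8)/15 = 0.44. The residual variance is 1.44 × 0.56 = 0.806 and the model SE is √(2 × 0.806/(3 × 144)) = 0.061 in both cases. Against true SEs of 0.052 and 0.073, type I error is about 0.02 and 0.10. For the effect of −0.4 on one vignette, power is about 60% and 57% rather than 73% and 45%.

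**The case for a change.** The strongest case for a change is that the contradiction is plain, sits in a primary hypothesis, and costs one sentence to correct. The dilution to d/3 is arithmetic, and the ratings needed for vignette-specific estimates are already being collected. On the illustration with an effect in one vignette only, the interaction test has far more power than the average.

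The contradiction stands, as does the difference between the two descriptions of Study 2, although injectable may simply be the shorter account of a study that also has an oral part. Neither affects an analysis.

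The averaging point is weaker. Section 2.0 sets Aim 3 on parents' acceptability scores, and section 10.2 scores exactly those after each study, so aim and endpoint match. Aim 3 does not ask whether the agent's effect depends on consent condition. The d/3 result also needs complete ratings and a mean model; if many responses lie at the boundary, section 10.4.1 moves to a median model, for which it need not hold. The favourable interaction power belongs to one chosen pattern, and across the assumed ranges the detectable spread varies almost fourfold.

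The direct item is largely explained by section 3.4.2 itself: the permission question can follow only the scenario that requires parental permission, which fits two or three questions per vignette. An item tied to one scenario could not serve a three-condition endpoint, and section 10.2 gives that reason for excluding other such items, though it does not name this one. What remains is an omission from Table 2.

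The dependence of type I error on the random-intercept assumption is a separate matter. It concerns the covariance structure, not the hypothesis wording or the averaging, and its size rests on correlations the documents do not give.

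**Conclusion.** No change to the plan is needed. The word topical is a clerical slip with no numerical effect: the Study 1 versus Study 2 contrast is the same under any label. When the protocol is next edited for another reason, the hypothesis and the Study 2 descriptions in sections 2.0, 3.0, 10.1 and Appendix I can be aligned. The consent forms (Appendix II) are not in the text reviewed, so which description they match is for the study team to say.

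The averaged parent effect answers Aim 3 as written. If the agent's effect is similar across vignettes, averaging is the more efficient choice: SE 0.052 to 0.073 against 0.089, assuming SD 1.2, r = 0.6, 144 parents and c from 0 to 0.5. If the effect lies in one vignette only, the average understates it, by a factor of three with complete ratings and a mean model. Analysts can show estimates by vignette as an exploratory description without a protocol change. A small average should not be read as a small effect under every consent condition.

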3.0 STUDY DESIGN

This study will use a quasi-experimental design to explore how the informed consent process affects the acceptability of biomedical HIV prevention trials, from the perspective of behaviorally high-risk minor adolescents and the parents of minor adolescents. All study participants will complete a computer assisted self-interview (CASI) that collects demographic, social, behavioral, and attitudinal measures. Adolescent participants will undergo a simulated consent process for each of two hypothetical studies based on their randomized consent condition (Appendix II). Parent Participants will undergo a simulated consent process that mimics what their own adolescent would hear while consenting for each of the two hypothetical studies. After each hypothetical study, parent participants will complete a CASI with three vignettes that describe each of the three possible consent conditions. Parents will rate the acceptability of each vignette. The order of vignettes, and the order of the two hypothetical studies, is varied to reduce the possibility of ordering bias. Hypothetical Study 1, modeled after ATN 113, is an open-label study of oral TDF-FTC and hypothetical Study 2, modeled after HPTN 077, is a Phase IIa trial of an injectable HIV integrase inhibitor.

Eligible adolescent participants will complete a demographic questionnaire, then be lead by RS through a simulated study consent process for one of two hypothetical studies. The consent process will be consistent with their randomly assigned consent condition. After completing the simulated consent process, the adolescent will complete a CASI assessing adolescents' WTP and will work with RS to complete the UCSD Brief Assessment of Capacity to Consent (UBACC)²⁵. The

simulated consent process and follow-up assessments will then be completed for the second hypothetical study. After the second UBACC, the adolescent will complete overall WTP, medical mistrust, and end of study questions.

Eligible parent participants will first complete a demographic questionnaire. They will then review the informed consent form for the first study with the RS and complete a CASI assessing the acceptability of three approaches to consent, presented in three different vignettes (please see section 3.4.2 for further information). Parents will work with RS to complete the UCSD Brief Assessment of Capacity to Consent (UBACC)²⁵. The simulated consent process and follow-up assessments will then be completed for the second hypothetical study. After the second UBACC, the participant will answer a series of questions via CASI.

A subset of adolescent and parent participants will be selected to participate in a debriefing interview.

3.1 Study Population

This study will recruit adolescents between ages 14-17, inclusive, who are able to read and speak English, who have a negative or unknown HIV status; and who have engaged in high-risk sexual activity (see **Table 1**) in the last 12 months. The study will also recruit adults who are able to read and speak English, who are a parent or guardian to an adolescent who is between ages 14-17, inclusive, and who have a negative or unknown HIV status. Adolescent and parent participants will be recruited from four U.S. cities: Baltimore, MD; Chicago, IL; Denver, CO; and Tampa, FL. These cities have diverse populations, high rates of incident HIV infection among adolescents and young adults, and/or demonstrated success in recruiting minor adolescents for biomedical HIV research. Recruitment will be primarily clinic-based, but if that method proves insufficient for recruiting participants, we will employ a variety of strategies for recruitment including: social media advertising, fliers, and word of mouth.

3.2 Sample Size

This study will enroll approximately 144 (36 per study site) high-risk minor adolescents and 144 (36 per study site) parents of adolescents. A subset of 24-32 (6-8 per study site) adolescents and 24-32 (6-8 per study site) parents will be selected to participate in the debriefing interview. Of note, the adolescents and parents will not be parent-child dyads; they will be unrelated. We project total enrollment of 288 participants, however, since this is a multi-site project with simultaneous recruitment with a hard to reach population, we may schedule and enroll more subjects than anticipated.

